### 9.1.3 Supportive Care, Guidelines for CNS toxicities

- **Central Nervous System Necrosis:**
  - For **Grade 2 events**, treat with systemic steroids, pentoxifylline and vitamin E. Consider starting with doses less than dexamethasone 6mg PO daily (2 mg TID), if clinically acceptable and indicated.
  - For **Grade 3-4 events**, immediately treat with intravenous steroids. Administer additional anti-inflammatory measures, such as hyperbaric oxygen and/or surgical intervention.
  - When symptoms improve to Grade 1 or less, steroid taper should be started immediately, continued over no less than 4 weeks.
  - It may be that a patient may need low doses of steroids long term, in that case, the goal is to achieve the lowest tolerated steroid levels to manage the radiation necrosis.
- **Seizure:**
  - For **Grade 1-2 events**, treat with oral anti-seizure medications. If clinically safe and acceptable, consider starting with levetiracetam 1000mg BID, or alternative.
  - For **Grade 3-4 events**, treat with oral and/or IV anti corticosteroids with consideration for surgery, if clinically feasible.
  - When symptoms improve to Grade 1 or less, steroid taper should be started and continued over no less than 4 weeks.
- **Cognitive Impairment or Cognitive Disturbance**
  - For **Grade 2 events**, treat with systemic steroids. Consider starting with doses less than 6 mg PO dexamethasone (2 mg TID), if clinically acceptable and indicated. Memantine or other Alzheimer related medication can also be considered.
  - For **Grade 3-4 events**, immediately treat with intravenous steroids.
  - When symptoms improve to Grade 1 or less, steroid taper should be started and continued over no less than 4 weeks.

## 10.0 DIET/ACTIVITY/OTHER CONSIDERATIONS

### 10.1.1 Diet

Subjects should maintain a normal diet unless modifications are required to manage an AE such as diarrhea, nausea or vomiting.

### 10.1.2 Contraception

Pembrolizumab may have adverse effects on a fetus in utero. Furthermore, it is not known if pembrolizumab has transient adverse effects on the composition of sperm. For this trial, male subjects will be considered to be of non-reproductive potential if they have azoospermia (whether due to having had a vasectomy or due to an underlying medical condition).

Female subjects will be considered of non-reproductive potential if they are either:

(1) postmenopausal (defined as at least 12 months with no menses without an alternative medical cause; in women < 45 years of age a high follicle stimulating hormone (FSH) level in the postmenopausal range may be used to confirm a post-menopausal state in women not using hormonal contraception or hormonal replacement therapy. In the absence of 12 months of amenorrhea, a single FSH measurement is insufficient.);

OR

(2) have had a hysterectomy and/or bilateral oophorectomy, bilateral salpingectomy or bilateral tubal ligation/occlusion, at least 6 weeks prior to screening;

OR

(3) has a congenital or acquired condition that prevents childbearing.

Female and male subjects of reproductive potential must agree to avoid becoming pregnant or impregnating a partner, respectively, while receiving study drug and for 120 days after the last dose of study drug by complying with one of the following:

(1) practice abstinence† from heterosexual activity;

OR

(2) use (or have their partner use) acceptable contraception during heterosexual activity.

Acceptable methods of contraception are‡:

Single method (one of the following is acceptable):

- intrauterine device (IUD)
- vasectomy of a female subject's male partner
- contraceptive rod implanted into the skin

Combination method (requires use of two of the following):

- diaphragm with spermicide (cannot be used in conjunction with cervical cap/spermicide)
- cervical cap with spermicide (nulliparous women only)
- contraceptive sponge (nulliparous women only)
- male condom or female condom (cannot be used together)

- hormonal contraceptive: oral contraceptive pill (estrogen/progestin pill or progestin-only pill), contraceptive skin patch, vaginal contraceptive ring, or subcutaneous contraceptive injection

†Abstinence (relative to heterosexual activity) can be used as the sole method of contraception if it is consistently employed as the subject's preferred and usual lifestyle and if considered acceptable by local regulatory agencies and ERCs/IRBs. Periodic abstinence (e.g., calendar, ovulation, sympto-thermal, post-ovulation methods, etc.) and withdrawal are not acceptable methods of contraception.

‡If a contraceptive method listed above is restricted by local regulations/guidelines, then it does not qualify as an acceptable method of contraception for subjects participating at sites in this country/region.

Subjects should be informed that taking the study medication may involve unknown risks to the fetus (unborn baby) if pregnancy were to occur during the study. In order to participate in the study subjects of childbearing potential must adhere to the contraception requirement (described above) from the day of study medication initiation (or 14 days prior to the initiation of study medication for oral contraception) throughout the study period up to 120 days after the last dose of trial therapy. **If there is any question that a subject of childbearing potential will not reliably comply with the requirements for contraception, that subject should not be entered into the study.**

### **10.1.3 Use in Pregnancy**

If a subject inadvertently becomes pregnant while on treatment with pembrolizumab, the subject will immediately be removed from the study. The site will contact the subject at least monthly and document the subject's status until the pregnancy has been completed or terminated. The outcome of the pregnancy will be reported to the Sponsor and to Merck without delay and within 24 hours to the Sponsor and within 2 working days to Merck if the outcome is a serious adverse experience (e.g., death, abortion, congenital anomaly, or other disabling or life-threatening complication to the mother or newborn).

The study investigator will make every effort to obtain permission to follow the outcome of the pregnancy and report the condition of the fetus or newborn to the Sponsor. If a male subject impregnates his female partner the study personnel at the site must be informed immediately and the pregnancy reported to the Sponsor and to Merck and followed as described above and in Section 13.2.2.

### **10.1.4 Use in Nursing Women**

It is unknown whether pembrolizumab is excreted in human milk. Since many drugs are excreted in human milk, and because of the potential for serious adverse reactions in the nursing infant, subjects who are breast-feeding are not eligible for enrollment.

## 10.2 Subject Withdrawal/Discontinuation Criteria

Subjects may withdraw consent at any time for any reason or be dropped from the trial at the discretion of the investigator should any untoward effect occur. In addition, a subject may be withdrawn by the sponsor-investigator if enrollment into the trial is inappropriate, the trial plan is violated, or for administrative and/or other safety reasons

A subject must be discontinued from the trial for any of the following reasons:

- The subject or legal representative (such as a parent or legal guardian) withdraws consent.
- Confirmed extra-cranial radiographic disease progression
- Unacceptable adverse experiences as described in section 7, 8, and 9.
- Intercurrent illness that prevents further administration of treatment
- Investigator's decision to withdraw the subject
- The subject has a confirmed positive serum pregnancy test
- Noncompliance with trial treatment or procedure requirements
- The subject is lost to follow-up
- Completed at least 24 months of uninterrupted treatment with pembrolizumab or 35 administrations of study medication, or whichever occurs last;  
*Note: 24 months of study medication is calculated from the date of first dose. Subjects who stop pembrolizumab after 24 months may be eligible for up to one year of additional study treatment at the discretion of their treating physician, especially if their disease is clinically stable;*
- Administrative reasons
- Confirmed radiographic disease progression per RECIST criteria.
  - a. *Note: A subject may be granted an exception to continue on treatment with confirmed radiographic progression if clinically stable or clinically improved, please see Section 6.5*

The End of Treatment and Follow-up visit procedures are listed in Section 12 (Protocol Flow Chart) and Section 13. After the end of treatment, each subject will be followed for 30 days for adverse event monitoring (serious adverse events will be collected for 90 days after the end of treatment as described in Section 13.2.3.1). Subjects who discontinue for reasons other than progressive disease will have post-treatment follow-up for disease status until disease progression, initiating a non-study cancer treatment, withdrawing consent or becoming lost to follow-up. After documented disease progression each subject will be followed by telephone for overall survival until death, withdrawal of consent, or the end of the study, whichever occurs first.

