All patients will have a baseline PET scan as well as a diagnostic CT chest, abdomen, and pelvis. All pre-treatment and post treatment imaging will be per standard of care for staging and surveillance purposes. They will also have a baseline brain MRI. Post SRS treatment, they will continue to have diagnostic brain MRI (at 6 weeks, and then every 3 months) as well as CT chest/abdomen/pelvis (every 3 months) per standard of care, to evaluate response and to monitor for any unexpected toxicity. Routine standard of care blood work (CBC, BMP, LDH, etc) will also be ordered at baseline and with all subsequent visits.

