**2.3 Acute Toxicity, Expansion Cohorts, and Late Toxicity Assessment:**

Once 6 patients are enrolled on any given dose level, there will be a waiting period of 3 months (i.e, at time of second post SRS MRI assessment after pembrolizumab dose (i.e, 3 months after Day 1, cycle 1); This time point of 3 months and the dose limiting toxicity (i.e. grade 3 RTOG CNS toxicity) is based on similar timeline used on earlier trial to determine the safest radiation dose. Late toxicity (radionecrosis noted on MRI images will also be analyzed at 6 months and at 1 year, but will not be used to stop enrollment on any given dose arm.);

During this 3 month waiting period, the MRI images and the patients will be assessed for any

signs or symptoms of RTOG CNS toxicity as well as early manifestations of radionecrosis.  $\geq$  Grade 3 CNS toxicity is the only DLT toxicity of principal concern. Patient can still be accrued on other dose arms during this waiting period, while data is being analyzed for safety concerns on a given radiation arm.

- If  $\leq 2/6$  patients develop a DLT on a given radiation arm, accrual on the particular dose arm will continue for another 6 patients for a total of 12 patients per dose arm. RTOG 90-05 used a 20% cutoff at 3 months as the DLT endpoint. We accept 2/6 (33%) based on a biological rationale that if there is slight increase in radiation toxicity, this may be offset by increased systemic responses through immune modulation of radiation when radiation is combined with anti PD-1 (see section 4.0 for biological rationale);
- If  $\geq 3/6$  patients develop a DLT on a given radiation dose arm, this arm will stop accrual and considered unsafe;

[figure not shown]
Late toxicity (i.e, toxicity starting after 3 months) will also be analyzed (a **secondary endpoint of trial**). The principal late toxicity of interest is symptomatic radiation necrosis. This is defined as radiographic (typically on MRI) changes consistent with radiation induced necrosis, and the patient also presenting with increased neurological symptoms. Symptomatic radiation necrosis will be recorded at 6 months and at 12 months;

- The radiation dose arm which meets the lowest DLT (i.e.  $\geq$  Grade 3 CNS Toxicity at 3 months) and late toxicity (any radiation necrosis) endpoints, but also potentially provides higher overall systemic response rate and OS, will be considered the best radiation dose level that can be combined with pembrolizumab.

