#### 11.1.10 Radiation Toxicity Evaluation

Patients should undergo evaluation for development of acute and chronic radiotherapy toxicity at the time of protocol visits. This should be done 1 month after completing SRS (between weeks 4-6 post SRS, per standard of care) and then during follow-up visits and maintenance therapy every 3 months, or as otherwise indicated. Suspected radiosurgery-related toxicity should be graded using the CTCAE 4.0 adverse events grading system. If there is a suspicion of a novel or unexpected toxicity of grade 3 or higher severity that is suspected to be related to the combination of pembrolizumab and radiosurgery, the study coordinator should be immediately notified. If possible, a determination should be made whether the toxicity is likely to be the result of immune therapy, radiosurgery or was exacerbated by the combination. The AE or SAE should be attributed as definite, probable, possible, or unlikely for each.

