##### **13.1.2.2 Enrollment and Treatment Period**

Enrollment period to accrue all 30 patients will be over two years, with the goal to enroll at least 18 patients, as outlined in section 2.0.

Treatment period will last from cycle 1, day 1 until disease progression and/or at least 12 months of pembrolizumab being delivered q3wks. Pembrolizumab 200 mg IV q3 weeks +/- 7 days will be given for at least 2 years as described above or until disease progression. Safety evaluations should be conducted during the first day of each cycle, as detailed in the flow sheet 12.0. All AEs that occurred leading up to these treatment visits should be recorded. Post-

Treatment Visits and all subsequent imaging and tumor assessments will be per standard of care. All required blood and imaging will be per standard of care, except for the biomarker analysis, as outlined in section 12.0.

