#### **13.1.2.3 Follow-up Visits**

Subjects who complete treatment after 2 years or discontinue trial treatment for a reason other than disease progression should be assessed every 12 weeks ( $84 \pm 14$  days) or at physicians' discretions by radiologic imaging to monitor disease. Subjects who show disease progression after the initial week 12 scan must have another assessment 4-6 weeks later by radiologic imaging to confirm evidence of disease progression. If disease progression is evident, treatment should be discontinued and subject should be assessed every 12 weeks ( $84 \pm 14$  days) by radiologic imaging to monitor disease status. Every effort should be made to collect information regarding disease status until the start of new anti-neoplastic therapy, disease progression, death, end of the study or if the subject begins retreatment with pembrolizumab as detailed in Section 6.5. Information regarding post-study anti-neoplastic treatment will be collected if new treatment is initiated.

Subjects who are eligible to receive retreatment with pembrolizumab according to the criteria in Section 6.5 will move from the follow-up phase to the Second Course Phase when they experience disease progression. Details are provided in Section 13.1.3.4 for Retreatment.

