#### **13.1.2.4.1 Survival Follow-up**

Once a subject experiences confirmed disease progression or starts a new anti-cancer therapy, the subject moves into the survival follow-up phase and should be contacted by telephone every 12 weeks to assess for survival status until death, withdrawal of consent, or the end of the study, whichever occurs first.

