#### **14.1.2 Acute Toxicity, Expansion Cohorts, and Late Toxicity Assessment:**

Once 6 patients are enrolled on any given dose level, there will be a waiting period of 3 months (i.e., at time of second post SRS MRI assessment after pembrolizumab dose (i.e., 3 months after Day 1, cycle 1)); This time point of 3 months and the dose limiting toxicity (i.e. grade 3 RTOG CNS toxicity) is based on similar timeline used on earlier trial to determine the safest radiation dose. Late toxicity (radionecrosis noted on MRI images will also be analyzed at 6 months and at 1 year, but will not be used to stop enrollment on any given dose arm);

During this 3 month waiting period, the MRI images and the patients will be assessed for any signs or symptoms of RTOG CNS toxicity as well as early manifestations of radionecrosis.  $\geq$ Grade 3 CNS toxicity is the only DLT toxicity of principal concern, since the currently used radiation doses are based on this primary endpoint. Patient can still be accrued on other dose arms during this waiting period, while data is being analyzed for safety concerns on a given radiation arm.

Late toxicity (i.e., toxicity starting after 3 months) will also be analyzed. The principal late toxicity of interest is symptomatic radiation necrosis. This is defined as radiographic (typically on MRI) changes consistent with radiation induced necrosis, and the patient also presenting with increased neurological symptoms. Symptomatic radiation necrosis will be recorded at 6 months at at 12 months follow-up;

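### Sections disagree on whether CNS toxicity is recorded after progression; necrosis missed this way would in effect count as event-free in the fixed denominator of 12 (or 6)

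*Combined protocol and SAP*

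**What the plan says.** Two sections end clinical follow-up at progression. Section 10.2: "After documented disease progression each subject will be followed by telephone for overall survival until death". Section 13.1.2.4.1: "Once a subject experiences confirmed disease progression or starts a new anti-cancer therapy, the subject moves into the survival follow-up phase", with a call every 12 weeks for survival status.

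Other sections continue:
- Section 13.1.2.3: "If disease progression is evident, treatment should be discontinued and subject should be assessed every 12 weeks" by radiologic imaging (the brain is not named).
- Section 2.1, after SRS: "they will continue to have diagnostic brain MRI (at 6 weeks, and then every 3 months".
- Section 11.1.10 places radiation-toxicity evaluation "during follow-up visits and maintenance therapy every 3 months, or as otherwise indicated", with no stop at progression.
- Section 13.1.1.7 has adverse events graded and recorded through the follow-up period.
- The flow chart (Section 12.1) marks brain MRI and adverse-effect assessment in the post-treatment column, and Grade 3 CNS at 3, 6 and 12 months. It makes no exception for progressed patients, and Section 10.2 itself refers to it for follow-up procedures.

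Imaging is not trial-specific. Section 13.1.2.2 says that "all subsequent imaging and tumor assessments will be per standard of care".

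On the endpoint, Section 2.3 says: "Symptomatic radiation necrosis will be recorded at 6 months and at 12 months". Section 14.1.2 repeats this. Section 3.2.3(e) requires MRI evidence together with attributable neurological symptoms. Section 14.3.1 reports late toxicity per arm out of 12, or 6 without expansion, with Clopper-Pearson limits and no rule for patients not assessed. Section 14.3.4 estimates radionecrosis and symptomatic radionecrosis by cumulative incidence with death competing, censored at salvage whole brain radiation and/or last follow-up.

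**The concern.** A survival call supplies neither an MRI finding nor a neurological assessment. The scans probably continue as standard of care. The risk is that their results, and the symptoms, are not entered for the trial once a patient is on telephone contact.

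With a fixed denominator, a patient whose necrosis is not recorded adds 0 to the numerator and 1 to the denominator. The reported proportion then falls below the true one, and the Clopper-Pearson interval does not allow for that. Late toxicity is one of the criteria in Sections 2.3 and 14.1.2 for naming the best radiation arm. A reader of the results could not tell no necrosis among 12 assessed patients from no necrosis among the few still assessed.

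**Working it through.** The plan gives no figure on this point to reproduce. The check has two parts.

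**1. What could be missed if the telephone text is followed**

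- Intracranial progression alone: Section 11.1.11 lets the patient stay on treatment until extra-cranial progression. The gap therefore mainly concerns extra-cranial progression.
- Any adverse event: Sections 10.2, 13.1.3.2.1 and 13.2 record to about 30 days after treatment. Section 13.1.1.7 and the flow chart carry recording through follow-up. This is a second inconsistency.
- Serious events: Section 13.2.3.1 captures any serious event to 90 days after treatment whether or not related to the drug, or to 30 days if new therapy starts. After that it captures only serious events judged related to the Merck product.

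This leaves exposed non-serious necrosis arising after about 30 days, and serious necrosis attributed to SRS after 90 days (30 days if new therapy starts).

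**2. Illustration of size (telephone branch only)**

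Inputs:
- 12-month necrosis risk absent death, 15%: an assumption. Section 4.0.3 cites 10-15% grade 3 toxicity with SRS, which is not a necrosis rate, so 10% is shown as well.
- 1-year survival, 78% or 38%: Section 2.3. Deaths are taken as independent of necrosis and progression.
- PFS, 22 or 14 weeks: Section 4.2.1, read as exponential medians. The source is ipilimumab-refractory melanoma, and Section 4.4.1 says brain metastases were excluded. NSCLC is not modelled.
- Scans at weeks 12, 24, 36 and 48, with confirmation 4-6 weeks later: Sections 13.1.2.3 and 6.5.

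Formulas, per week:
- a = -ln(0.85)/52 = 0.003125
- b = -ln(OS)/52 = 0.004778 (OS 78%) or 0.018607 (OS 38%)
- Observable necrosis by week t: F(t) = a/(a+b) x (1 - exp(-(a+b)t)). F(52) = 13.33% (OS 78%) or 9.74% (OS 38%).
- Reported rate = sum over scans s of P(progression first detected at s) x F(min(s+d, 52)), plus P(not detected by week 48) x F(52). Here d is the number of weeks from the scan to the end of recording.

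Worked case, OS 78%, median 14 weeks, d = 8:
- Detection probabilities at weeks 12, 24 and 36 are 0.448, 0.247 and 0.137. The remaining 0.168 is observed to week 52.
- F(20) = 5.78%, F(32) = 8.84%, F(44) = 11.62%, F(52) = 13.33%.
- Reported = 0.448 x 5.78 + 0.247 x 8.84 + 0.137 x 11.62 + 0.168 x 13.33 = 8.60%.
- Gap = 13.33 - 8.60 = 4.7 points.

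12-month gaps in percentage points:

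| Recording ends | OS 78%, 22 wk | OS 78%, 14 wk | OS 38%, 22 wk | OS 38%, 14 wk |
|---|---|---|---|---|
| Confirmation scan (d = 4-6) | 3.94-4.28 | 5.15-5.58 | 2.38-2.63 | 3.13-3.44 |
| About 30 days later (d = 8-10) | 3.26-3.60 | 4.31-4.72 | 1.92-2.14 | 2.55-2.84 |
| About 90 days later, serious necrosis, no new therapy (d = 17-19) | 1.91-2.16 | 2.60-2.93 | 1.06-1.22 | 1.45-1.66 |

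The ranges are 2.4-5.6, 1.9-4.7 and 1.1-2.9 points. The middle row is 0.2 to 0.6 of a patient in 12 (0.019 x 12 to 0.047 x 12).

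Sensitivity, with recording ending at the confirmation scan:
- A 10% risk gives 1.6-3.8 points, so the gap moves almost in proportion to the assumed risk.
- If half of the progressors are still recorded, the gap halves to 1.2-2.8.
- If deaths occur only after progression (simulation), it is 1.3-5.4.
- At 6 months it is 0.5-1.2.

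For Section 14.3.4 (simulated Aalen-Johansen estimates at week 52, recording ending at the confirmation scan):
- Follow-up to the last telephone contact gives 7.7-9.4% (OS 78%) and 6.3-7.3% (OS 38%).
- Censoring at the last CNS assessment gives 13.2-13.4% and 9.7-9.9%, close to the true 13.3% and 9.7%.

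**The case against.** The strongest case on the other side is that the plan, read as a whole, does collect the data. The flow chart and Sections 2.1, 11.1.10 and 13.1.1.7 carry CNS and toxicity assessment forward without an exception for progression, and patients with intracranial progression may stay on treatment. Section 14.3.4 already names symptomatic radionecrosis for a competing-risk analysis. Necrosis is a secondary endpoint and cannot stop an arm. The effect is under one patient in 12.

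Much of this stands and limits the weight of the point. It does not settle which text a site follows after extra-cranial progression. The flow chart has no row for necrosis. Section 14.3.4 is not ranked above Section 14.3.1, and its end of follow-up could be read as the last telephone contact.

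A reader might infer more than the documents support:
- That CNS follow-up does stop at progression. The sections conflict, so this is one branch only.
- That SRS-attributed necrosis is lost as soon as the 30-day window closes. Section 13.2.3.1 captures any serious event to 90 days if no new therapy starts.
- That the SAP directs unassessed patients to be scored event-free. It gives no such rule; this is the arithmetic effect of the fixed denominator.
- That the comparison of arms is distorted. This would require progression or recording to differ by arm, which is not shown.

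**Conclusion.** The conflict between sections is real, and the documents do not resolve it. If the telephone text is applied, the 12-month necrosis proportion in Section 14.3.1 is biased downward. The illustrative size is about 1.9-4.7 points when adverse-event recording runs 30 days past the confirmation scan, 2.4-5.6 when it stops at that scan, and 1.1-2.9 for serious necrosis under the 90-day rule.

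These figures rest on an assumed 15% risk, constant hazards and a PFS proxy from a different population, so the direction is firmer than the size. Against a 12-patient interval such as 2.1% to 48.4% for 2/12, the bias is small. It is still worth removing, because it runs one way and the interval does not reflect it. Severity: minor.

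**What to change.** 1. Reconcile Sections 10.2, 13.1.2.4.1, 13.1.2.3, 2.1, 11.1.10, 13.1.1.7 and the flow chart. They should state that 6- and 12-month CNS toxicity data, taken from standard-of-care brain MRI and visits, are recorded to 12 months, death or withdrawal of consent, regardless of progression or new therapy. This concerns data recording only; no imaging or treatment rule is proposed.
2. For late necrosis, make the Section 14.3.4 cumulative incidence, with death competing, the reported estimate. Define last follow-up for this endpoint as the last CNS assessment. Show the number assessed at 6 and 12 months per arm beside any raw count kept from Section 14.3.1.

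The cost is protocol and SAP wording, plus some extra abstraction from scans and visits already done. Censoring at the last CNS assessment may still be informative if recording stops for reasons linked to necrosis risk; the number assessed lets a reader judge that.
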